2.2.1 KNOWN POTENTIAL RISKS

- **Study drug:** Caffeine is one of the most frequently used medications in the NICU for infants born very preterm. At the time of enrollment, infants will be tolerating routine caffeine treatment without any adverse clinical effects. However, known potential side effects of caffeine, would include:
 - Transient decreased weight gain
 - Tachycardia
 - Gastrointestinal symptoms, including feeding intolerance
 - Jitteriness
 - Hypertension
- Each of these side effects would be expected in fewer than 5% of participants.
- **Pulse oximeter recordings:** Pulse oximetry is routinely used in the NICU and sometimes also indicated for home use. The study oximeter will be in addition to the comparable oximeter routinely used clinically. We will follow routine clinical routines for frequent site relocation of the oximeter sensors (probes), to decrease the risk of significant skin irritation.
- **Blood sampling for inflammatory biomarkers:** There will be 2 blood samples obtained, one at enrollment and the 2nd prior to NICU discharge, and the blood volume for each sampling will be <1 ml. Whenever possible, these blood samples will be obtained as part of a clinically indicated routine heel stick or venipuncture, thus decreasing the need to cause infant discomfort beyond that required for routine clinical management.
- **Brain MRI:** All MRIs performed for this study will be done without sedation, thus eliminating the most important potential risk beyond that associated with a clinically-indicated brain MRI. However, the time required for each study MRI will be more than that required for a routine brain MRI.
- **Salivary samples:** The 2 salivary caffeine samples for each subject will be obtained using a commercially available salivary collection kit identical to that used in our recent pilot study. These salivary collections are easily obtained and have not been associated with any infant discomfort or parental concern.
- **Loss of confidentiality** is also a potential risk. However, all demographic and clinical information will be entered in a secure password-protected database accessible only to the research staff at that

clinical site and the data coordinating center (DCC) at Boston University Medical Center. Clinical site research staff will enter data via web access. Identifiers that have been collected will be stored separately from research data. The data will be in a separate locked/password protected database linked only by a subject ID number. Identifiers collected for the purpose of performing follow-up will be stored in a separate database that will be destroyed after the study is completed. The data will be split as it is loaded; personal identifiers (names, addresses, telephone numbers) will be entered into the tracking database along with a unique numeric identifier, and other data (excluding the participants' names and address) will be stored in the analytic database. It will be possible to link information in these two databases only through a coded numeric identifier; it will not be possible to identify individual participants in the analytic database. The separation of names and addresses from personal data adds an important level of security and helps to assure that participant confidentiality will be maintained. Follow-up data will be processed in a similar manner. The analytic database will contain no identifiers and will be the exclusive source for all data analyses performed at the DCC. Database files will be stored at the DCC on network servers located in a data center at the Slone Epidemiology Center at Boston University. Slone Epidemiology Center data center is a separate secure room monitored by key access. Activity on the Slone network and servers is monitored by a University security team. In addition, access to the Slone network is restricted by specific Virtual Private Network group access and router access control lists. Servers are protected by software firewalls and enterprise antivirus software. Administrators to the servers are limited to a core group of individuals who oversee server health and security. Network access to the servers is protected by requiring a user to login to an Active Directory system using the assigned username and Kerberos password. Access to directories and files are restricted by user membership to network security groups. Network security group membership is granted only if a user is affiliated with a research study or group. When a user is not affiliated with any research study or group, access is denied and removed. Backup data is taken at regular intervals. This backup data is encrypted and stored in a secure off-site facility for three years. Any request for file restoration is examined, monitored, and documented. After three years, backup data is verified and certified for destruction. Any websites used by Slone for data collection are protected with SSL protocols—commonly referred to HTTPS. These protocols provide encrypted communication and secure identification of web servers using certificates. Certificates are signed by trusted certificate authority.

- Recurrence of Apnea-related symptoms in placebo-treated subjects: We have not observed any recurrent apnea-related symptoms in preliminary studies after stopping routine caffeine.^{18,90} However, if a subject has apnea-related clinical symptoms after stopping routine caffeine and starting study drug, nasal CPAP or nasal cannula may be used as needed at the discretion of the clinical team. After the last dose of study drug at 42 weeks + 6 days PMA, pulse oximeter recordings will be continued for 1 additional week, to 43 weeks + 6 days PMA, for those participants enrolled at sites at which home oximetry is included in the study. No significant alarms have occurred after stopping extended caffeine treatment in our pilot studies, and none are anticipated in this clinical trial since at this PMA the extent of **IH** no longer differs from healthy term infants .^{15,16} However, the oximeter alarms can be activated for this final study week if deemed necessary by the clinical site investigator.

2.2.2 KNOWN POTENTIAL BENEFITS

Direct Potential Benefits:

- Infants randomized to receive extended caffeine treatment may benefit directly by having less intermittent hypoxia and hence less inflammation and improved brain MRI findings

- Placebo-treated infants will benefit from the additional support and information provided by research staff, and will have the potential for benefit from information obtained from the MRI evaluations, which would not have been done absent enrollment in this study. Except for the inflammatory biomarkers and brain MRIs, placebo-treated enrollees are equivalent to “usual care” clinical practice in NICUs today.

General Future Potential Benefits:

- This study will fill several major gaps in our current knowledge: 1) The impact on neurodevelopmental outcome of the frequency and severity of **IH** in the NICU and at home until 43 weeks PMA, assessed by continuous pulse oximeter recordings of oxygen saturation and heart rate, 2) the frequency and severity of **IH** in preterm infants receiving caffeine vs. placebo while in the NICU, 3) the frequency and severity of **IH** persisting at home after discharge (for participants receiving home oximetry), and 4) the efficacy of continuing caffeine treatment until 42 weeks + 6 days PMA with regard to reducing **IH** and improving neurodevelopment.
- Infants randomized to caffeine may benefit from improved neurodevelopmental outcome related to attenuated **IH** during the period of exposure to study drug.

2.2.3 ASSESSMENT OF POTENTIAL RISKS AND BENEFITS

- The risk: benefit ratio is favorable
- Extending caffeine treatment to 42 weeks + 6 days PMA has the potential of improving brain structure and function as determined by MRI, and improving neurodevelopmental outcomes.
- Infants randomized to placebo will be receiving what is currently the standard of care when their last routine caffeine dose is between 32 weeks + 0 days PMA and 36 weeks and 5 days PMA.
- The potential risks are primarily related to blood sampling and the brain MRIs. As discussed above, however, the blood samples will be obtained as a part of clinically indicated blood sampling, and the MRIs will be performed without sedation.
- In summary, the potential benefits exceed the potential risks of participation in this study, and there are no increased risks if randomized to receive placebo since placebo infants will otherwise be receiving the same clinical care as comparable infants not enrolled in this study.

3 OBJECTIVES AND ENDPOINTS

OBJECTIVES	ENDPOINTS	JUSTIFICATION FOR ENDPOINTS
Primary		

Primary Objective 1: Compare the extent of IH exposure, from randomization through 42 weeks + 6 days PMA (within each gestational week and overall), in infants randomized to extended caffeine treatment to infants assigned to receive placebo.
 
Primary Objective 2: Compare changes in a panel of inflammation-related cytokines and chemokines, from enrollment to the target age of 38 weeks + 0 days PMA, in infants randomized to extended caffeine treatment to infants assigned to receive placebo.
 
Primary Objective 3: Compare changes in quantitative MRI structural, microstructural and metabolic biomarkers of acute injury, from enrollment to 43-46 weeks PMA, in infants randomized to extended caffeine treatment to infants assigned to receive placebo.
	
# of sec of IH <90% at each PMA week
 
Change in plasma concentration of each inflammatory biomarker from baseline to 38 weeks PMA.
 
Difference between neuroimaging measures at baseline and at 43-46 weeks PMA, including diffusion tensor imaging (DTI) and proton magnetic resonance spectroscopy (MRS).
	
# of sec of IH <90% the most representative measure to quantitate extent of IH
 
Measuring biomarker concentrations at 38 weeks will be a sufficient interval for changes since baseline, and will be the interval during which differences in extent of IH will be maximal.
 
Quantitative MRI is a sensitive modality for assessing structural, biochemical, and functional changes consequent to IH and extent of improvement with extended caffeine treatment. Assessing at study end will provide maximal time for adverse MRI changes consequent to IH since starting study drug.

Secondary		

Secondary Objective 1: Examine the association between salivary caffeine concentrations and IH outcomes at the one week post randomization and 40 weeks + 0 days PMA assessments.
 
Secondary Objective 2: Determine whether changes, from baseline to follow-up, in
	
Extent of IH (# of sec <90%) paired with saliva caffeine level during PMA week of oximetry recording.
 
Change in plasma concentration for each inflammatory
	
# of sec of IH <90% is the most representative measure of extent of IH during the week corresponding in time to the caffeine level.
 
See above

OBJECTIVES	ENDPOINTS	JUSTIFICATION FOR ENDPOINTS
inflammatory or MRI biomarkers are mediated by caffeine-related reduced IH .	biomarker, from baseline to 38 weeks PMA, in relation to IH measures. Change in each MRI parameter, from baseline to 43-46 weeks PMA in relation to IH measures.	

4 STUDY DESIGN

4.1 OVERALL DESIGN

HYPOTHESES:

Hypothesis 1: Caffeine will reduce extent of **IH** compared to placebo, and this caffeine effect will persist to 42 weeks PMA.

Hypothesis 2: Extended caffeine treatment will be associated with less acute inflammation at 37-38 weeks compared to placebo, and these effects will be mediated by attenuated **IH**.

Hypothesis 3: Quantitative MRI analyses in the active caffeine group, compared to the placebo group, will be associated with **1)** greater white matter microstructural organization, **2)** improved neuronal metabolism, and **3)** greater regional brain volume, and that these effects will be mediated by attenuated **IH**.

TYPE/DESIGN OF TRIAL:

Randomized, placebo-controlled, double-blinded clinical trial

METHODS TO BE USED TO MINIMIZE BIAS:

All clinical team personnel and all research staff (except research pharmacist) will remain blinded to study group until study completion. Caffeine and equal volume placebo will be prepared by research pharmacist and will be equivalent in color and consistency. The protocol has been designed such that there should be no need to break the code for any individual subject.

NUMBER OF STUDY GROUPS/ARM & STUDY INTERVENTION DURATION:

Infants will be randomized in a 1:1 ratio to 1 of 2 treatment arms, caffeine base (Arm 1) and placebo (Arm 2). Infants from multiple births will be cluster randomized. The duration of the intervention will be from randomization between 32 weeks + 0 days PMA and 36 weeks + 6 days PMA through 42 weeks + 6 days PMA, the age at which extent of **IH** no longer differs from healthy infants born at term.

MULTI-SITE STUDY:

There will be enrollment at multiple hospitals across the U.S.

NAME OF STUDY INTERVENTION:

Caffeine versus placebo

INTERIM ANALYSIS: None planned

STRATIFICATION:

A site-stratified randomly-permuted blocked randomization design will be used to ensure balance at each site. To ensure balance by gestational age at birth, randomization will also be stratified into 2 birth gestational age categories: 1) <28 weeks 2) 28 weeks + 0 days through 30 weeks + 6 days. The randomization scheme will be developed by the DCC using specialized software, and clinical sites will be provided appropriate enrollment logs and randomization procedures from the research pharmacy.

SUB-STUDIES: No ancillary studies planned at this time

4.2 SCIENTIFIC RATIONALE FOR STUDY DESIGN

Our pilot studies have demonstrated that **IH** associated with immature breathing pattern in infants born preterm can be attenuated with caffeine. It is unknown, however, whether persisting **IH** after stopping routine caffeine treatment in the NICU, which may only evident with continuing high resolution pulse oximetry, results in any long-term injury. The results in the group randomized to extended caffeine treatment (Arm 1) will be compared to placebo (Arm 2) to determine if extended caffeine treatment is superior to placebo in attenuating or eliminating the adverse effects of persisting **IH** on inflammation and brain MRI structural, microstructural, and metabolic markers of injury.

4.3 JUSTIFICATION FOR DOSE

Infants will be started on oral caffeine base at 5 mg/kg/day or equivalent volume of placebo. At 36 weeks + 0 days PMA, study drug dose will be increased to 5 mg/kg BID (total daily dose 10 mg/kg) or equivalent volume of placebo. The dose will be weight-adjusted weekly until NICU discharge. The starting dose and dose escalation at 36 weeks + 0 days PMA reflect increasing clearance rates that have been established in pilot studies as being appropriate to achieve caffeine levels within the most likely therapeutic range. All subjects will be on enteral medications when enrolled.

4.4 END OF STUDY DEFINITION

Each subject will be considered to have completed the study after the planned pulse oximeter recording data is completed and inflammatory biomarker samples are provided, and if applicable, has completed the outpatient brain MRI between 43 weeks + 0 days and 46 weeks + 6 days PMA, as shown in the Schedule of Activities (SOA), Section 1.3.

5 STUDY POPULATION

5.1 INCLUSION CRITERIA

INCLUSION CRITERIA:

In order to be eligible to participate in this study, an individual must meet all of the following criteria:

1. Male and female infants born preterm at \leq 30 weeks + 6 days postmenstrual age
2. Current treatment with routine caffeine. Note infants will meet this inclusion criteria through the third calendar day following receiving their most recent routine caffeine dose.
3. PMA 32 weeks + 0 days - 36 weeks + 6 days
4. Anticipated last dose of routine caffeine will be by 36 weeks + 5 days
5. At least 12 hours of **breathing room air** with no ventilatory support other than on **room air** nasal air flow therapy regardless of flow rate, or on **room air** and receiving nasal CPAP, and relapse not anticipated.
6. Able to tolerate enteral medications
7. It is feasible to administer the first dose of study drug no later than 36 weeks + 6 days PMA

5.2 EXCLUSION CRITERIA

EXCLUSION CRITERIA:

1. Intraventricular hemorrhage Grade III-IV or cystic periventricular leukomalacia
2. Current or prior treatment for seizures
3. Current or prior treatment for cardiac arrhythmias
4. Known renal or hepatic dysfunction that in the opinion of the investigator would have a clinically relevant impact on caffeine metabolism
5. Major malformation, inborn error of metabolism, chromosomal abnormality
6. Presence of a condition for which survival to discharge unlikely
7. Social, mental health, logistical or other issues that, in the opinion of the investigator, would impact the ability of the family to complete the study.

5.3 LIFESTYLE CONSIDERATIONS

- Parents and clinical care providers will be asked to avoid exposure to caffeine for subjects.
- Open label treatment with a methylxanthine will be documented.
- There will be no restrictions on maternal diet even if breast feeding.

5.4 SCREEN FAILURES

- Screened and potentially eligible infants for enrollment will be screen failures if they reach 36 weeks + 6 days PMA and are still receiving routine caffeine or, for whatever reason, cannot be enrolled by 36 weeks + 6 days PMA.
- Enrolled infants will be screen failures, and will not be randomized, if they do not continue to meet eligibility criteria at the time that routine caffeine treatment is being discontinued.
- Analysis will be by “intention to treat,” and all randomized subjects will remain included in their Arm for analysis.

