9.3 POPULATIONS FOR ANALYSES

The intention-to-treat (ITT) population will consist of all randomized subjects.

The modified intention-to-treat (mITT) population will include all subjects who took at least one dose of study drug and who have data available for efficacy outcomes.

The safety population will consist of all randomized subjects who receive a dose of study drug.

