9.4.2 ANALYSIS OF THE PRIMARY EFFICACY ENDPOINTS

Primary Objective 1: Compare the extent of **IH** exposure, from randomization through 42 weeks + 6 days PMA (within each gestational week and overall), in infants randomized to extended caffeine treatment to infants assigned to receive placebo.

Analyses for this objective will be performed on the mITT population and compare those randomized to extended caffeine vs. placebo. To be included in **IH** analyses, a subject must have had at least 10 hours of acceptable quality oximetry data recorded within at least one PMA week. A single overall baseline SaO_2

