Analyses for this objective will be performed on the mITT population and compare those randomized to extended caffeine vs. placebo. To be included in the analyses a subject must have had a baseline/follow-up pair of blood samples for which at least one biomarker was measured on both samples. Analysis will focus on change in inflammatory biomarker levels over the study period. Preliminary analyses will examine the distribution of biomarkers, and data will be transformed (e.g., logged) as appropriate for analysis. Two approaches will be taken for the primary analyses, comparing changes in biomarkers over the study period in extended caffeine vs. placebo infants. First, we will conduct separate analyses of each inflammatory biomarker using linear regression models to compare study groups at study completion, controlling for baseline levels as well as key covariates including morbidities that might be associated with inflammation, using the Benjamini and Hochberg method to account for multiple testing by controlling the false discovery rate. Second, we will examine the structure of the biomarker data using data reduction procedures of factor analyses (identifying latent variables reflected by the set of biomarkers) and latent profile analysis (identifying subgroups of infants with similar patterns of biomarker profiles). Extended caffeine vs. placebo infants would then be compared on the summary measures of inflammation biomarkers resulting from these analyses.

Primary Objective 3: Compare changes in quantitative MRI structural, microstructural and metabolic biomarkers of acute injury, from enrollment to 43-46 weeks PMA, in infants randomized to extended caffeine treatment to infants assigned to receive placebo.

Analyses for this objective will be performed on the mITT population and compare those randomized to extended caffeine vs. placebo. To be included in the analyses a subject must have had a baseline/follow-up pair of MRI studies completed from which at least one MRI endpoint could be measured on both assessments.

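### Section 5.4 promises intention-to-treat on all randomized infants, but all three primary analyses use a population that depends on dosing and data, and the ITT analysis is only a conditional fallback

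*Combined protocol and SAP*

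**What the plan says.** Section 5.4 (Screen Failures) ends by committing the trial to intention to treat and says that "all randomized subjects will remain included in their Arm for analysis".

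Section 9.3 separates two efficacy populations. On the first: "The intention-to-treat (ITT) population will consist of all randomized subjects". The second, mITT, is "all subjects who took at least one dose of study drug and who have data available for efficacy outcomes".

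Section 9.4.2 assigns the second set to Primary Objectives 1, 2 and 3 in the same words each time: "Analyses for this objective will be performed on the mITT population and compare those randomized to extended caffeine vs. placebo". Each objective then adds a data condition:

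- Objective 1 (intermittent hypoxia): "a subject must have had at least 10 hours of acceptable quality oximetry data recorded within at least one PMA week".
- Objective 2 (inflammatory biomarkers): "a subject must have had a baseline/follow-up pair of blood samples", with at least one biomarker measured on both.
- Objective 3 (MRI): a baseline and a follow-up scan, with at least one endpoint measurable on both.

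The ITT population reappears only in section 9.4.1, as the basis for a multiple-imputation sensitivity analysis to be done if loss to follow-up is above 10%.

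**The concern.** A reader of section 5.4 expects every randomized infant in the primary comparison, while a reader of section 9.4.2 finds a set conditioned on dosing and on having data. Nothing in the protocol reconciles the two. If this stays open until the data are unblinded, the choice of primary population could be made with the results in view.

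The fallback does not close the gap, because its trigger counts a different kind of loss from the one that removes infants from the analyses. The pair rule also drops infants whose follow-up outcome was observed, although the planned models use baseline only as a covariate.

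**Working it through.** **1. The texts side by side.**

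| Place | Population | Requires a dose? | Requires data? |
|---|---|---|---|
| 5.4 | all randomized | no | no |
| 9.3, ITT | all randomized | no | no |
| 9.4.2, Objective 1 | mITT | yes | yes: 10 hours of oximetry in one PMA week |
| 9.4.2, Objective 2 | mITT | yes | yes: blood-sample pair |
| 9.4.2, Objective 3 | mITT | yes | yes: MRI pair |
| 9.4.1, sensitivity | ITT | no | imputed, but only if loss exceeds 10% |

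No primary analysis uses the set named in 5.4.

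**2. The trigger.** Section 7.3 defines loss to follow-up as failing to return for the end-of-study visit and being unreachable. Of 220 randomized infants, 10% is 22, so more than 22 must be lost in that sense before the ITT analysis runs. An infant who completes the final visit but lacks a blood sample or a usable scan is not lost under 7.3, yet leaves the Objective 2 or 3 analysis. Exclusions from those analyses can therefore pass 10% without triggering the ITT analysis.

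**3. Size of the dosing condition.** The plan's power figure comes first. Section 9.2 gives 82% for n = 100 per group and a standardized difference d = 0.50, at a familywise two-sided 0.05. The number of weekly tests k is not stated; weeks 36 to 42 give k = 7. With a Bonferroni first step and the normal approximation:

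- power = Φ(d·√(n/2) − z), where z is the two-sided critical value at 0.05/k
- k = 7: Φ(0.50·√50 − 2.690) = Φ(0.846) = 80.1%
- k = 6 gives 81.5% and k = 5 gives 83.1%

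The stated figure is reproduced to within 2 points.

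Now suppose (assumed) that 3 undosed infants per arm, showing no effect, join 100 per group. Then d = 0.50 × 100/103 = 0.485, and power for k = 7 is Φ(0.485·√51.5 − 2.690) = 78.6%. That is a loss of about 1.5 points.

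**4. Size of the pair rule.** Sections 9.4.2 (Objectives 2 and 3) compare end-of-study values with baseline as a covariate. If a fraction m of infants with an observed follow-up lack only the baseline, dropping them multiplies the standard error by at most 1/√(1 − m):

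| m (assumed) | 1/√(1 − m) | Inflation, at most |
|---|---|---|
| 5% | 1.026 | 2.6% |
| 10% | 1.054 | 5.4% |
| 15% | 1.085 | 8.5% |

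These are upper bounds, because a retained infant with an imputed baseline carries less information than one with a measured baseline. MRI, with a goal of 55 infants per arm (section 8.1.3), has the least room for such a loss.

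**5. When baseline availability is settled.** Section 8.1.2 places the first blood sample before randomization. Footnote 3 of the Schedule of Activities (1.3) allows it up to the second calendar day after the first dose. Footnote 4 allows the first MRI up to three calendar days after study drug starts. Whether an infant has a baseline can thus be decided after randomization, but within days and under blinding.

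**The case against.** The best defence is that 5.4 means only that infants are analysed in the arm to which they were randomized, which 9.4.2 respects, and that a bullet under Screen Failures was never meant to define the analysis set. On this view one corrected sentence is enough. It is true that one sentence would remove the contradiction. But 5.4 says that all randomized infants stay included, and 9.3 shows that the authors distinguish ITT from mITT.

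The pair rule also has a rationale: Objectives 2 and 3 are stated as changes from enrollment, and an infant without a baseline has no observed change. That stands as an explanation, but the ANCOVA that is actually planned does not need an observed change. Section 9.4.2 (under Secondary Objective 1) also provides for multiple imputation if missing data become a problem. It names no population and no criterion, so it helps only in part.

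Three stronger readings are tempting, and the documents do not support them:

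- **That the trial would report as ITT something it did not run.** Section 9 labels the primary population mITT openly.
- **That the pair rule undoes the randomization.** A missing baseline is settled before assignment or shortly after it, under blinding, so the likely cost is precision rather than bias.
- **That all 220 infants belong in every primary analysis.** MRI is planned in about half of them, at participating sites (8.1.3). The rest are never scheduled for a scan, and imputing their scans would serve no purpose. Home oximetry that is absent at non-participating sites (8.1.1) is likewise missing by design.

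For Objective 1 there is no pair rule, and inpatient recording is planned for every infant. Entry to that analysis should therefore be close to complete; missing later weeks are a separate matter.

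**Conclusion.** The concern holds as a contradiction in the current text, together with a fallback whose trigger does not match the exclusions it should cover. It should be corrected, but it does not threaten the trial's validity.

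The dosing condition should matter little, since treatment is blinded and the first dose is planned for the day of randomization. The pair rule inflates standard errors by at most about 3% to 9% for Objectives 2 and 3, if 5% to 15% of infants with follow-up lack only the baseline. That range, and the 3 undosed infants per arm in the power check, are assumptions; the documents give neither rate. The contradiction itself rests on no figure.

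**What to change.** Make 5.4, 9.3 and 9.4.2 name the same primary population before unblinding:

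1. **Primary analysis.** Analyse infants as randomized, whether or not dosed, including every infant with an observed post-randomization outcome for that objective. For Objective 3, restrict this to infants randomized at MRI sites. Reword 5.4 to match.
2. **Objectives 2 and 3.** Replace the pair rule with imputation of a missing baseline covariate in the ANCOVA already planned.
3. **Sensitivity analyses.** Run the multiple-imputation ITT analysis unconditionally, without the 10% trigger and with the same MRI-site restriction. Keep the current mITT and pair-based set as a further sensitivity analysis.
4. **Baseline blood sample.** Reconcile 8.1.2 with footnote 3 of section 1.3 on its timing.

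The cost is a little more analysis work and a very slight dilution from any undosed infants. No new data collection is needed.
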